Pragmatic trial design. For an RCT of a self-guided online intervention, it is important that the design mimics intended intervention use (Fleming et al., 2018). As examples, overly stringent inclusion criteria limit generalizability, or face-to-face assessments may provide added benefit beyond the intervention itself (Fleming et al., 2018). Therefore, as much as possible our methods simulate how a real-world campus might offer online services as usual. First, we are employing cluster randomization, for reasons elaborated below. Second, participants in either condition will be allowed to access other on- or off-campus mental health services and resources; in our statistical analyses we will control for service use rather than excluding such students. Third, all data collection and participant communications will be electronic rather than in-person to: (a) include all students remote or on-campus, (b) avoid unintentionally bolstering motivation (e.g., inducing social desirability to please researchers), and (c) avoid adding barriers (e.g., time demands, concerns about privacy). Finally, survey compensation

amount will be modest enough to increase participant response rates without artificially inflating adherence rates or self-reported improvement due to financial incentive.

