Random assignment. Cluster randomization will be used to assign students according to their residential affiliation to the **immediate intervention condition** or the **waitlist condition** (i.e., delayed access). This randomization plan has been discussed with the Dean of Students Office and was preferred over a fully randomized assignment of students. Although cluster randomization can introduce statistical confounds for analyzing intervention outcomes at the individual participant level, they can be preferred: (a) to avoid intervention “contamination” effects (e.g., if participants in both conditions can regularly interact and thus might exchange health-related knowledge), and (b) if it allows the intervention to be delivered as it would be in real practice (Cook, Delong, Murray, Vollmer, & Heagerty, 2016). Moreover, the benefits of cluster randomization by residential house/dorm affiliation for this trial are crucial for the social aspects of the StriveWeekly program. For example, students will know who else is concurrently participating in the program (e.g., any of their friends in X, Y, Z house), allowing for peer-to-peer engagement. Also, this will allow for easier coordination of any optional complementary programming by residential staff at each house/dorm. A randomizer was already used to assign half the freshmen and upperclassman residential buildings to each condition:

Immediate StriveWeekly Access	Delayed StriveWeekly Access
Houses: Adams, Cabot, Currier, Dudley, Mather, Quincy, Winthrop	Houses: Dunster, Eliot, Kirkland, Leverett, Lowell, Pforzheimer
Freshmen: Ivy Yard, Elm Yard	Freshmen: Crimson Yard, Oak Yard, Maple Yard

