Every Monday participants receive an email directing them to the instructions section of the online platform. Each module presents a checklist of activities for participants to complete as well as tips and suggestions for how to practice each module's skill. At the beginning of the week, participants make a "plan" indicating which activities/skills they intended to try and any barriers they expected to encounter. Throughout the week, participants can visit their user dashboard to log skills practice for the current module (within a seven-day grace period) along with ratings of their mood and stress levels, which are plotted in their self-monitoring graph. NOTE: Students do not complete any of the activities within the app (e.g., users do not record their unhelpful thinking habits during week 3), but rather they submit a log after practicing a skill outside of the app. At the end of each module participants are prompted to complete weekly check-in questions about their personal goal progress. Weekly prize drawings (items of \$10-40 value) will be offered to all participants submitting a weekly check-in. Students who had log activity for all modules will be eligible for the completer prize drawing (items of \$100-200 value).

There is also a "Campus" section of their dashboard that provides students with: info about relevant campus resources; a notification center with campus-specific messages and updates; and an anonymous livestream of all campus users' activity, to provide a sense of community. See screenshots of the online platform in the **Supplemental Materials** uploaded.

Finally, residential staff will be encouraged to offer complimentary programming (e.g., relevant themed study breaks), if they are so interested in doing so. These events will not involve any data collection, but the PI will contact residential staff (through approved coordination with the Dean of Students office) to document which houses/dorms held additional events, so that such information can be treated as a covariate in data analyses.

Waitlist group. Participants in this group will receive no intervention or communications between their baseline randomization and the invitation for posttest survey. They will be provided access to the online program after completing the posttest survey.

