The below sections contain additional questions depending on the type of research that you are conducting and is meant to supplement the study overview. Please complete each section, as applicable.

SURVEYS/ QUESTIONNAIRES/PSYCHOMETRIC TESTING

Skip this section if not applicable.

5.2 List the names of all surveys/questionnaires/psychometric tests to be used in this study and a description of any that are not standard/formally named (such as study-specific questionnaires).

See full details in uploaded measure battery.

1. **Self-report demographic questionnaire** (age, gender, ethnicity, academic year).
2. **Branding feedback.** There will be a few questions about if students would have been more or less likely to sign-up for the program had it been under a different name (e.g. "The Happiness Challenge")
3. **Treatment Motivation Questionnaire (TMQ).** Questions from the Treatment Motivation Questionnaire (Ryan, Plant, & O'Malley, 1995) have been minimally adapted to apply to an online mental health promotion program instead of a treatment. Questions from the help-

seeking subscale were removed. This 20-question measure will assess participants' reasons for signing up and expectations for completing the program. The TMQ has significant predicted intervention completion in other research studies, for example in-person alcohol treatment (Ryan et al., 1995) and online trauma treatment (Alfonsson et al., 2016).

4. **Depression Anxiety and Stress Scale.** The primary symptom outcome measure will be the 21-item version of the Depression Anxiety and Stress Scale (DASS-21), which assesses self-reported symptoms related to depression, anxiety, and stress. The DASS-21 has demonstrated high internal consistency (.83 - .90) and good construct validity in university student samples (Norton, 2007). Note: There are no questions related to suicidality.
5. **Perceived Stress Scale.** This measure is a 10-item scale that is the most widely used psychological instrument for measuring the perception of stress. It is a measure of the degree to which situations in one's life are appraised as stressful. Items were designed to tap how unpredictable, uncontrollable, and overloaded respondents find their lives.

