Study title: Randomized Controlled Trial (RCT) of StriveWeekly for Anxiety and Depression Prevention for College Students During COVID-19

NCT #:NCT04927845

Document date: 06/01/2023

The following “Data analysis” section is an excerpt from a proposal titled “Randomized Controlled Trial of StriveWeekly during COVID-19” that was submitted on 08/14/2020 to Harvard University Foundations of Human Behavior Initiative Proposal.

Data analysis. For assessing intervention effects, piecewise LME models will be run in predicting change in outcome scores. Included variables of group, time, group by time interaction, and covariates will be treated as fixed effects, whereas participant intercepts and outcome slopes will be allowed to vary randomly. Between-group and with-group effect sizes (d) will be calculated based on estimated marginal means. Moderator and mediator analyses will be selected *post hoc*, based on data completeness. Given the number of exploratory analyses that will be conducted, all significant findings will be tested against Benjamini-Hochberg critical values, on order to control for false discovery rate (i.e., Type I error).

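### The outcome model commits to neither building type (freshman yard or upperclass house) nor building type by time, although yards split 2 to 3 between the arms

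*SAP*

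**What the plan says.** The SAP (Data analysis) states that "piecewise LME models will be run in predicting change in outcome scores". For the terms, "Included variables of group, time, group by time interaction, and covariates will be treated as fixed effects", while "participant intercepts and outcome slopes will be allowed to vary randomly". This is the only model specification in either document, and the SAP does not list the covariates.

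The Protocol names two covariates, both in 5.1. Under Pragmatic trial design, "in our statistical analyses we will control for service use rather than excluding such students". Under Intervention group, extra events run by residential staff are to be recorded "so that such information can be treated as a covariate in data analyses". Academic year, a close individual-level stand-in for building type, is collected in the demographic questionnaire (5.2: "age, gender, ethnicity, academic year") but is given no place in the model.

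On allocation, the Protocol (5.1, Random assignment) says: "A randomizer was already used to assign half the freshmen and upperclassman residential buildings to each condition". The table below that sentence has separate rows for houses and freshman yards. The immediate arm has 7 houses and 2 yards. The delayed arm has 6 houses and 3 yards ("Freshmen: Crimson Yard, Oak Yard, Maple Yard"). Residential affiliation is recorded for every participant during electronic consent (9.2).

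**The concern.** The allocation sentence and the table layout suggest that buildings were drawn within type. When assignment is restricted by a factor, the analysis would normally carry that factor. Even if the draw was not restricted, building type is known before any outcome and is unevenly spread over the arms when buildings are counted.

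The main hypothesis (Protocol 4.1) concerns change from baseline in September to posttest in November. If first-year students change differently from older students over those weeks, an arm with more freshmen shows a different average change for a reason unrelated to the program. The group-by-time contrast would absorb that difference.

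Leaving the covariates open does not settle the matter. An analyst who later adds building type or academic year as an ordinary main effect would adjust for level and leave the contrast in change where it was. Only the interaction with time acts on it.

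**Working it through.** The documents give no sample size, power or enrolment by building, so there is no planned figure to reproduce.

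**1. Counts (Protocol 5.1 table).** Immediate: 7 houses + 2 yards = 9 clusters. Waitlist: 6 houses + 3 yards = 9 clusters. With 13 houses and 5 yards, 7 to 6 and 2 to 3 are the closest splits possible.

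**2. Does the split prove a draw within type?** Under an unrestricted 9:9 draw, the chance of this split or its mirror is 2 × C(5,2) × C(13,7) / C(18,9) = 2 × 10 × 1,716 / 48,620 = 0.706. The split alone therefore shows nothing; the case rests on the sentence and the table layout.

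**3. Freshman share by arm.** Input: about 6,000 undergraduates (Protocol 7.1). Assumptions: four equal classes, equal building sizes within type, equal uptake.
- Per yard: 1,500 / 5 = 300. Per house: 4,500 / 13 = 346.
- Immediate: 600 / (600 + 2,423) = 19.8%.
- Waitlist: 900 / (900 + 2,077) = 30.2%.
- Gap: 10.4 points.

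Sensitivity of the gap:
- Freshmen enrolling at half the upperclass rate: 17.8% − 11.0% = 6.8 points. At twice the rate: 46.4% − 33.1% = 13.3 points.
- Unequal building sizes (lognormal, 200,000 draws), 95% range: 6.6 to 14.2 points at a coefficient of variation of 10%, 2.7 to 18.0 at 20%, and −1.1 to 21.8 at 30%. At 30% the gap reverses in 3.7% of draws.

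**4. Shift in the contrast.** Shift = gap × difference in mean change between freshmen and upperclass students (assumed 0.1 to 0.5 SD, either direction). The last column compares it with the earlier trial's d = 0.25 (Protocol 4.2).

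| Difference in change (SD) | Shift (SD) | Share of 0.25 |
|---|---|---|
| 0.1 | 0.010 | 4% |
| 0.2 | 0.021 | 8% |
| 0.3 | 0.031 | 12% |
| 0.5 | 0.052 | 21% |

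**5. Which term removes it?** Noise-free generalized least squares in a three-wave piecewise model. Segments are coded (0,1,1) and (0,0,1), with random intercept and slopes (assumed variances 0.5, 0.2 and 0.1, covariance −0.05, residual 0.3). The true effect is −0.25, the same in both building types. Estimated group-by-time contrast with complete data:

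| Freshman difference (SD) | Listed terms | + building type | + building type by time |
|---|---|---|---|
| −0.5 | −0.198 | −0.198 | −0.250 |
| −0.2 | −0.229 | −0.229 | −0.250 |
| +0.2 | −0.271 | −0.271 | −0.250 |
| +0.5 | −0.302 | −0.302 | −0.250 |

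The first column follows by hand: −0.25 − 0.1039 × 0.5 = −0.302. A time-invariant term takes the same amount off a student's baseline and posttest, so it cancels from the change. Posttest loss that differs by building type moves the first two columns slightly. With 40% loss in freshmen and 25% in others, at +0.5, the three values are −0.296, −0.298 and −0.250.

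**6. Price of the extra terms.** Without a cluster term, the student-level correlation of arm and freshman status is 0.120. The variance inflation is 1 / (1 − 0.120²) = 1.0146, so the standard error is multiplied by 1.007. With clusters modelled, the correlation is 0.124 in size, the inflation 1.0156 and the multiplier 1.008. Between-cluster degrees of freedom fall from 16 to 15 (t from 2.120 to 2.131), so the interval widens by 1.0078 × 2.1314 / 2.1199 = 1.013.

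**The case against.** The strongest reply is that the documents show no harm. The shift is the product of a student-level gap and a difference in change, and neither is reported. The gap is inferred from building counts and could vanish; the difference in change is assumed. The SAP's open reference to covariates could also include building type or academic year. Once houses and yards are modelled, chance differences in their composition enter the standard error, which leaves mainly a preference for conditional balance and efficiency. All of this stands, and it limits the point to a minor one.

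Four stronger readings are tempting but unsupported:
- That allocation was stratified and the analysis ignores its strata. The Protocol never says stratified, and the split is common under an unrestricted draw.
- That the comparison is biased by design. Random assignment is valid, and the direction of any imbalance in change is unknown.
- That the SAP excludes building type. It only fails to commit to it.
- That the shift is some stated fraction of a standard error. With no sample size or variance components given, and the answer depending on whether clusters are modelled, no such ratio can be supported.

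The reply does not dispose of the time interaction. A covariate list filled in later with main effects would leave the contrast exposed, as step 5 shows.

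**Conclusion.** The point holds as a modest gap in specification. No section commits to building type or to building type by time, although the Protocol describes assignment by halves of the freshman and upperclass buildings. With equal class sizes, equal building sizes within type and equal uptake, the freshman gap is 10.4 points. For an assumed difference in change of 0.1 to 0.5 SD, the contrast then moves by about 0.01 to 0.05 SD, toward or away from benefit. Both inputs are assumptions, and the true shift may be close to zero. The exact recovery of −0.250 also assumes the same treatment effect in both building types. The missing house or yard effect in the same model is a separate and more important matter.

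**What to change.** In the piecewise mixed model, add building type (freshman yard or upperclass house, coded from the affiliation given at consent) and its interaction with each time segment as fixed effects. Leave the other planned terms as they are. State whether the draw was made separately within yards and within houses.

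Timing affects the label. The SAP text comes from a proposal dated 08/14/2020, the document carries the date 06/01/2023, and the Protocol's timetable places the last survey in April 2022. The documents do not say whether outcomes had been analysed. If they have been, report this model as a labelled sensitivity analysis and do not describe it as prespecified.

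The cost is two sentences and no new data. The standard error widens by 0.7% in the model as listed. If clusters are modelled, the interval is about 1.3% wider and one between-cluster degree of freedom is used.

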7. CHARACTERISTICS OF THE STUDY POPULATION

7.1 Indicate the estimated number of participants, by subgroup if applicable. If it is not possible to estimate the number of participants (e.g., open online survey), please indicate that it is not possible and provide an explanation of why it is not possible.

It is not possible to estimate how many participants will enroll, as it will be open to all Harvard undergraduate students who are interested in enrolling. The maximum sample size therefore cannot exceed the size of the undergraduate student body (~6000). By contrast, the randomized controlled trial at UCLA enrolled 1600+ students from an entire student body of 40,000+. This programming was not centrally sponsored by an equivalent to the Dean of Students Office though, so we expect the relative enrollment rate to be higher by percentage of enrolling students relative to total student body. The secondary analyses on a subset of survey data is estimated to include approx. 125 students endorsing identification with the LGBTQ+ community. We expect to conduct follow up interviews with approximately 20 to 30 participants to achieve saturation.

7.2 Describe the criteria for enrollment – Will you be limiting your enrollment to a certain age range, gender, people with certain health conditions, etc.? Please also describe any criteria that will exclude people from enrollment.

We will recruit undergraduate students who are currently enrolled as fulltime students at Harvard as of the time of recruitment. There are no *a priori* exclusion criteria. *Post hoc* exclusion procedures will remove students with invalid data reporting (e.g., straight-lined responses to surveys, high inconsistency in responses to cross-validation item pairs selected based on content similarity). Additionally, inclusion criteria for secondary analyses assessing outcomes among sexual and gender minority subgroups will include endorsement of belonging to the LGBTQ+ community. Students eligible to participate in the follow up interviews will be those who (a) used the StriveWeekly platform at least

once, (b) completed all study surveys, and (c) either identify as LGBTQ+ or want to provide feedback about program inclusivity for this community.

7.3 Are there any potential vulnerable populations or individuals proposed for involvement in the research? (check all that apply)

- Children
- Wards of the State
- Prisoners/Detainees
- Pregnant Women
- Adults not Competent to Consent

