9. SCREENING

9.1 Will you be screening participants for eligibility? Note that If you are using inclusion or exclusion criteria, you will be "screening" individuals in order to determine who is eligible.

Yes

No (*skip to next section*)

9.2 Explain what your screening criteria will be and how you will conduct the screening process.

Participants will automatically be screened for current enrollment status using survey logic on Qualtrics. The Qualtrics consent form is configured to only be accessed by people with active HarvardKey access. Moreover, the electronic consent process will ask students to select their current residential affiliation, and if a participant does not select one, they will be redirected to a page informing them that they are not eligible.

9.3 Do you plan to destroy the data from people who participate in the screening process and do not qualify to be in the study as soon as the screening process is over?

Yes

No (*see below*)

If "No" explain why you will keep the data collected in the screening process for people who are not eligible to participate in this study.

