11.2 What type of compensation will you provide to participants?

Cash
 Check
 Gift Card/Gift Certificate
 Course Credit
 Lottery/Raffle (*see below*)
 Other (*see below*)

If you chose “Lottery/Raffle”:

What is the amount and total number of payments to be awarded?

\$5 Amazon gift card guaranteed for every survey. Pending approval, we may also give students the option of payment via CrimsonCash instead of Amazon.com gift card

For the full RCT, there will also be an additional raffle of x10 extra \$50 gift card for every survey. Participants can only win the raffle once. 4 surveys x 10 winners each time = 40 students earning the additional raffle gift card

For follow up interviews, participants who have met inclusion criteria and completed an individual interview will be guaranteed an additional \$15 Amazon gift card.

What are the odds of winning (if known)?

Odds of winning will depend on how many total participants complete each survey, and are expected to improve over time at each survey assessment. We estimate that odds of winning a bonus \$50 gift cards over the course of the study is 1:10 to 1:25.

What is the approximate timing of the drawing?

Winners will be notified and receive this gift card electronically within two weeks of submitting their respective full survey response, for each survey.

How will participants who are awarded be notified?

Email sent from Qualtrics or directly from Amazon.com, with PI's contact info provided

If you chose "Other" please specify:

Participants will have opportunities to earn prizes through StriveWeekly program participation during either Fall or Spring semester. Conceptually, these prize incentives are for supporting students' participation in the intervention. These prize drawings are not connected with the research surveys, so not all research participants would be entered. Therefore, these prizes are not counted within a participant's total research compensation payment amount.

Rather, these drawings are additional opportunities to earn prizes by those students who are actively participating in the StriveWeekly program. A random number generator will be used to select winners from the pool of eligible participants, according to these requirements:

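### Eighteen houses and yards are randomised, but the SAP model has random effects for participants only, so the group-by-time test is anti-conservative if symptom change is correlated within house or yard

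*SAP*

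**What the plan says.** Protocol 5.1, Random assignment: "Cluster randomization will be used to assign students according to their residential affiliation". It adds that "A randomizer was already used to assign half the freshmen and upperclassman residential buildings to each condition". The table there lists 7 houses and 2 freshman yards for immediate access, and 6 houses and 3 freshman yards for delayed access. The same paragraph concedes a drawback ("Although cluster randomization can introduce statistical confounds for analyzing intervention outcomes at the individual participant level") but names no analytic step to deal with it.

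SAP, Data analysis: a piecewise linear mixed model with group, time, group-by-time and covariates as fixed effects, "whereas participant intercepts and outcome slopes will be allowed to vary randomly". Exploratory findings are held to Benjamini-Hochberg critical values.

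The only house-level variable mentioned is whether a house or dorm held extra events. It is to be recorded (Protocol 5.1, Conditions) "so that such information can be treated as a covariate in data analyses".

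On size, Protocol 7.1 says "It is not possible to estimate how many participants will enroll". No ICC, numeric alpha or power calculation appears in either document.

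**The concern.** The effectiveness claim in Protocol 4.1 rests on the difference between arms in change from baseline to posttest. The randomised unit is the house or yard, so the uncertainty of that difference has to include variation in change between houses and yards. The SAP model treats students in the same house as independent, given their own intercept and slope. Any shared house trend is then counted as if it were independent information from each student.

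Only correlation of *change* does this. Stable differences in symptom level between houses cancel from the group-by-time contrast and cause no inflation.

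Correlated change is plausible here. The protocol chose clustering partly so that students in a house could take part together and residential staff could run related events, and students in both arms share ordinary house life. It is not established: the platform is self-guided and house events are optional. The plan neither estimates the correlation nor protects against it.

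**Working it through.** **The plan's own figure.** There is none to reproduce, because no sample size, power, alpha or ICC is given.

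**Inputs from the documents**
- Clusters (Protocol 5.1): 7 + 2 = 9 immediate and 6 + 3 = 9 delayed, 18 in all.
- Sample size: not stated. Protocol 11.2 plans 4 surveys x 10 winners = 40 raffle winners and puts the odds of winning "over the course of the study is 1:10 to 1:25". This implies 40 x 10 = 400 to 40 x 25 = 1,000 students, or m = N/18 = 22.2 to 55.6 per cluster.
- Lower benchmark (Protocol 7.1): the earlier trial enrolled 1,600 of 40,000, or 4%; 4% of about 6,000 is 240. The protocol expects a higher rate.
- Effect size (Protocol 4.2): d = 0.25 in the earlier trial, used only for power.

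**Assumptions.** Two-sided 5%; equal cluster sizes; ICC of change from 0 to 0.05; d = 0.25 taken in SD units of change.

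**Could anything in the plan already absorb the correlation?**
- Participant random slopes are independent between students of one house, so they cannot carry a shared trend.
- The event covariate removes only the part of the correlation that the events cause.
- The other covariates are not listed. House fixed intercepts would leave house-level change unmodelled, and a full set of house-by-time fixed terms would be collinear with group-by-time.
- Benjamini-Hochberg takes the too-small p-values as its input.

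**Type I error when clusters are ignored**

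DE = 1 + (m - 1) x ICC

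True error = 2 x [1 - Phi(1.96 / sqrt(DE))]

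At ICC 0.01:
- N = 400: DE = 1 + 21.22 x 0.01 = 1.212; 1.96/1.101 = 1.78; error 7.5%.
- N = 1,000: DE = 1 + 54.56 x 0.01 = 1.546; 1.96/1.243 = 1.58; error 11.5%.

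| ICC of change | N = 400 | N = 1,000 |
|---|---|---|
| 0 | 5.0% | 5.0% |
| 0.001 | 5.2% | 5.6% |
| 0.005 | 6.2% | 8.2% |
| 0.01 | 7.5% | 11.5% |
| 0.02 | 10.1% | 17.5% |
| 0.05 | 17.2% | 31.0% |

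**Variations**
- Correlation in one arm only, DE = 1 + (m - 1) x ICC/2: 6.2% to 8.2% at ICC 0.01; 11.3% to 20.2% at 0.05.
- 70% retention (assumed), so m is multiplied by 0.7: 6.7% to 9.5% at 0.01; 13.6% to 24.9% at 0.05.
- N = 240: 6.4% at 0.01; 12.3% at 0.05.
- Unequal clusters (simulated at N = 600, size CV 0.4): 9.4% at 0.01 and 24.8% at 0.05, against 8.8% and 23.2% with equal clusters.

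**Check by simulation.** With 18 equal clusters in the 7/6 and 2/3 layout, an individual-level test of change agreed with the formula to within about 0.3 percentage points. A t-test on the 18 cluster mean changes, adjusted for freshman v upperclass (15 df), stayed between 4.8% and 5.2% at N = 240, 400 and 1,000. The one exception was correlation in one arm only at ICC 0.05 and N = 1,000, where it gave about 5.4%.

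**The case against.** The strongest reply is that the harm is conditional. Nothing in the documents fixes the ICC of change, and for self-reported symptoms in an unguided programme it could be close to 0. At 0.001 the inflation is trivial, and if the correlation arises only through the programme the one-arm figures are the relevant ones. This stands as a limit on the size. It does not rescue the model, which is valid only if the ICC is 0 and offers no way to find out.

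Second, the SAP text is an excerpt from a funding proposal submitted on 08/14/2020, while the protocol describes the 2021-2022 academic year and an allocation already drawn. The excerpt may predate the cluster design, and a fuller plan may exist. But it is the only analysis plan supplied, and it goes as far as specifying the random effects without including the randomised unit.

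Third, Protocol 5.1 speaks of buildings while its table lists houses and yards. If dorms within yards were drawn separately, there are more than 18 units, and the degrees of freedom and permutation counts change. The table supports 18, and the missing cluster term stands either way.

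Fourth, tests on cluster mean changes use only students with both surveys, whereas the mixed model can also use those with baseline only. That is a fair reason to keep them as fallback and check, not as the main analysis.

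**Conclusion.** The concern holds. The analysis as written does not match the unit of randomisation, and nothing else in either document makes up for it. Given two-sided 5%, equal clusters and 400 to 1,000 students, a nominal 5% test has a true error of 7.5% to 11.5% at an ICC of change of 0.01 and 17.2% to 31.0% at 0.05; it stays at 5.0% if the ICC is 0. Confidence is high on the omission and on the direction of the error. The size cannot be pinned down without the ICC and N. Because the trial's main claim depends on this test, the SAP must be corrected.

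**What to change.** **Main model.** Nest participants in house/yard. Add a house/yard random intercept and a house/yard-by-time random effect, with the latter covering the baseline-to-posttest segment of the piecewise model. Add fixed terms for freshman v upperclass and its interaction with time. Test group-by-time with a Kenward-Roger or Satterthwaite correction, on about 15 to 16 between-cluster df. The event covariate is itself at cluster level and would use about one more.

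**If the fit is singular.** Do not return to the participant-only model. Use a t-test on the 18 house/yard mean changes, adjusted for freshman v upperclass, and state that it uses students with both surveys.

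**Check.** Run a permutation test on the 18 mean changes. If allocation was drawn separately for freshman and upperclass units, as Protocol 5.1 reads, permute within them: C(13,7) x C(5,2) = 1,716 x 10 = 17,160 allocations. Otherwise use all C(18,9) = 48,620. State which applied, and confirm that the table's houses and yards were the units drawn. Report the ICC of change.

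**Cost.** A few sentences and no new data. Protocol 9.2 says "the electronic consent process will ask students to select their current residential affiliation"; consent forms are stored apart from survey responses (12.18), so confirm that a house/yard code reaches the analysis dataset. Intervals widen by the factor sqrt(DE) x t(0.975; 15 or 16 df)/1.96. Power below is for d = 0.25, from the noncentral t with SE = sqrt(4 x DE/N).

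| ICC of change | Interval wider by (N = 400 to 1,000) | Power, N = 400 | Power, N = 1,000 |
|---|---|---|---|
| 0 | 8% to 9% | 65% | 96% |
| 0.01 | 19% to 35% | 57% | 84% to 85% |
| 0.05 | 55% to 110% | 37% | 48% to 49% |

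Beyond the 8% to 9% due to the degrees of freedom, the widening is uncertainty that the current model leaves out.
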